## 6.4. ANALYSIS PERIOD

The following analysis periods are defined for this study:

- Pre-treatment period = Date of Preliminary Visit (Day 0) to Date of first dose - 1
- On-treatment period = Date of first dose to Date of last dose inclusive +1
- Post-treatment period = End of last dose +1 days to End of study date

### Treatment Period for Adverse Events:

#### Pre-Treatment AE's:

An AE will be said to be pre-treatment AE if  
AE Start Date < Study Treatment Start Date

#### Treatment Emergent Adverse Event:

An AE will be defined as Treatment emergent adverse event (TEAE) if the AE start date is on or after treatment start date & on or before treatment stop date +1

Study Treatment Start Date ≤ AE Start Date ≤ Study Treatment Stop Date +1

If the last dose of study drug is missing and the AE start date is on or after the first dose of study drug, then the AE will be considered as TEAE

If the AE start date is missing or partial then the AE will be considered TEAE unless there is evidence to the contrary (e.g. month/year of onset date is present and is earlier than the month/year of first dose of study medication).

#### Post Treatment AE's:

An AE will be defined as post treatment AE if the AE start date is after the treatment stop date

AE Start Date > Study Treatment Stop Date +1

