3. OBJECTIVES AND ENDPOINTS

The objectives and endpoints of the study are provided in [Table 2](#) below:

Table 2 Objectives and Endpoints

Objectives	Endpoints
Primary	Primary

 The primary objective of the study is to assess treatment-emergent adverse events (TEAEs) in children receiving Augmentin (ES)-600 (AMC/CVA 14:1) at 90/6.4 mg/kg/day in two divided doses, administered for 10 days in ARTIs(AOM, ABRS or CABP). 	
 Safety will be evaluated by assessing the incidences of treatment emergent adverse events (TEAE).[§]

 The secondary objective of the study is to assess clinical efficacy and incidence of protocol defined diarrhoea (PDD)* in children receiving Augmentin (ES)-600 AMC/CVA 14:1 at 90/6.4 mg/kg/day in two divided doses administered for 10 days in ARTIs (AOM, ABRS or CABP). 	
 Efficacy assessment* will be based on: 
 Early clinical response at the on-therapy visit (Day 3 to 5), defined in terms of 'success' or 'failure' to study intervention. Primary clinical response at the end-of-therapy visit (Day 12 to 14), defined in terms of 'success' or 'failure' to study intervention Secondary clinical response at follow-up (day 22 to 28) ie, 'success' or 'failure'. Incidence of protocol-defined diarrhea (PDD)** in children receiving Augmentin (ES)-600 (AMC/CVA 14:1) at 90/6.4 mg/kg/day in two divided doses administered for 10 days in ARTIs (AOM, ABRS or CABP).

[§]A treatment-emergent adverse effect (TEAE) is defined as an AE which has its onset date on or after treatment start date and on or before treatment stop date + 1 day. All adverse events (AEs) experienced during the same period will be monitored. The detail is described in Section 8.3 “Adverse Events and Serious Adverse Events”.

**Protocol-defined diarrhoea is:

- 3 or more watery stools in one day OR
- 4 or more loose/watery stools in one day OR

- 2 watery stools per day for two consecutive days OR
- 3 loose/watery stools per day for two consecutive days.

* Efficacy assessment will be made using following criteria:

- **Early or Primary Clinical Response**

Success	Clinical cure	Sufficient resolution or improvement of the signs and symptoms such that no additional antibiotic therapy is indicated.

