#### 16.1.1. TEAES: PRIMARY SAFETY ENDPOINT

AEs occurring from when a subject sign informed consent to when a subject exits the study will be accounted for in the reporting. AEs occurring pre-treatment, treatment emergent adverse event (on-treatment) and post-treatment periods will be summarized and listed for the ITT population. A treatment -emergent adverse event is defined as any adverse event that develops after initiation of the study treatments or any adverse event already present that worsens following exposure to study treatment.

The primary safety endpoint will be summarized with counts and percentage of subjects reporting any TEAEs and subjects with at least one or any TEAE with corresponding 95% CI using exact binomial method

The following summaries will be generated for adverse events:

- Adverse event overview by period
- Adverse event overview by period for acute otitis media (AOM)
- Adverse event overview by period for acute bacterial rhinosinusitis (ABRS)
- Adverse event overview by period for community acquired bacterial pneumonia (CABP)
- Treatment emergent adverse events by system organ class, preferred term, overall and indication
- Adverse events by system organ class, preferred term, overall and indication - post-treatment
- Common ( $\geq 1\%$ ) treatment emergent adverse events by preferred term, overall and indication
- Common ( $\geq 1\%$ ) adverse events by preferred term, overall and indication - post-treatment

AEs and TEAEs will be sorted by descending order of system organ class (SOC) and total frequency of preferred term (PT) within each system organ class (SOC).

AEs and TEAEs related to study drug will be presented in decreasing order of preferred term (PT). Subjects listing of adverse events by indication (TEAE and post-treatment period) will be produced.

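### SAP 6.4 gives two different first days for the post-treatment period, so an AE starting the day after the last dose can be classed as both a TEAE and a post-treatment AE

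*SAP*

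**What the plan says.** SAP 6.4 first lists general analysis periods. For treatment: "On-treatment period = Date of first dose to Date of last dose inclusive +1". For what follows: "Post-treatment period = End of last dose +1 days to End of study date".

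It then sets rules specific to AEs. An event is a TEAE if its "AE start date is on or after treatment start date & on or before treatment stop date +1", repeated as a formula: "Study Treatment Start Date ≤ AE Start Date ≤ Study Treatment Stop Date +1". Under the post-treatment heading the words are "An AE will be defined as post treatment AE if the AE start date is after the treatment stop date", and the formula on the next line is "AE Start Date > Study Treatment Stop Date +1".

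The TEAE window itself is consistent. Protocol Section 3 defines a TEAE by "onset date on or after treatment start date and on or before treatment stop date + 1 day", and the one-day lag recurs in the Protocol Synopsis, Protocol 9.4.2 and 10.5.1, and SAP 16.1.

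SAP 16.1.1 uses these periods in its outputs. They start with "Adverse event overview by period", for all children and for each indication, followed by separate TEAE and post-treatment tables. SAP 16.1.1.1 does the same for maximum severity, and SAP 16.1.3 for serious AEs.

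**The concern.** The two post-treatment statements are on consecutive lines and cannot both hold. One starts the period on the first day after the last dose. The other starts it a day later, once the lag day has closed. Because the lag day is already inside the TEAE window, the sentence places an event with that onset in two categories meant to be separate.

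Safety is the primary objective, and the periods organise most of the AE reporting. SAP 2.2 also attaches a different estimand strategy to each side of the boundary: while-on-treatment for TEAEs and treatment policy for post-treatment AEs. One event should not fall under both. Two programmers working independently, one from the sentence and one from the formula, would produce different post-treatment tables from the same data.

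**Working it through.** No figure in the plan needs reproducing. The check is to apply each rule as written to AE start dates around the treatment stop date. Only the offset from the stop date matters, so Day 10 is used as an illustrative stop.

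Rules applied, all from SAP 6.4, with d = AE start day and s = stop day:

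- TEAE rule (words and formula agree): 1 ≤ d ≤ s + 1
- On-treatment period: 1 ≤ d ≤ s + 1
- Post-treatment period, natural reading: d ≥ s + 1
- Post-treatment AE, sentence: d > s
- Post-treatment AE, inequality: d > s + 1

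| AE start | TEAE rule | On-treatment period | Post-treatment period | Post-treatment sentence | Post-treatment inequality |
|---|---|---|---|---|---|
| Day 10 (stop) | yes | yes | no | no | no |
| Day 11 (stop + 1) | yes | yes | **yes** | **yes** | no |
| Day 12 (stop + 2) | no | no | yes | yes | yes |

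The rules disagree on one day only, stop + 1. The TEAE column is yes on that day whichever post-treatment rule is used.

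If all three post-treatment rules become d > s + 1, Day 11 is a TEAE only and Day 12 is post-treatment only. There is no gap or overlap, and the TEAE column is unchanged.

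The number of events starting on stop + 1 is not given. The most one affected child can add to a post-treatment incidence can be shown, assuming the analysis population reaches the planned numbers in SAP 6.8: 1/310 = 0.32 percentage points overall, 1/136 = 0.74 for acute otitis media, 1/106 = 0.94 for rhinosinusitis and 1/68 = 1.47 for pneumonia. The addition is smaller, or nil, if the child already counts in that row.

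**The case against.** The strongest reply is that the rule a programmer would code is already right. The three AE inequalities in SAP 6.4 (before start; start to stop + 1; after stop + 1) are mutually exclusive and, for complete dates, exhaustive. The concomitant-medication rules in the same section use the same stop + 1 boundary. That stands: double classification is something the wording permits, not something that must happen. It also shows which reading was intended.

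A second reply is that the general post-treatment line can be read as starting when the last-dose-plus-one-day interval ends, which would match the inequality. That reading is possible but less natural. It does not help with the AE-specific sentence, which conflicts with its own formula in any case.

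A third reply is that these outputs are descriptive, no hypothesis is tested (Protocol 9.1) and all AEs are listed (SAP 16.1), so a duplicate could be traced. This limits the harm but does not make the two lines consistent.

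Stronger readings are tempting, and the documents do not support them:

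- A reader might infer that a lag-day event could drop out of the primary endpoint. That would need a program to let the looser post-treatment sentence override the explicit TEAE rule, which has its own inequality and agrees with the protocol.
- A reader might take the lag day's share of the TEAE window as the size of the error. With a last dose on Day 10 or 11 the window is 11 or 12 days, so the share is 1/12 to 1/11, or 8.3% to 9.1%. With a last dose on Days 3 to 5 it is 4 to 6 days, so 1/6 to 1/4, or 17% to 25%. These become shares of events only if onset is uniform over the window, which no document states. They also count events, whereas the endpoint counts children. They do not measure any change in the primary estimate.
- A reader might suppose that children stopped early are especially likely to have onset on the lag day. The documents give no onset data. What prompts withdrawal is already present at the visit where it is assessed (Protocol 4.1 and 5.4.3.3), which gives no ground for expecting extra onsets the day after the last dose.

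**Conclusion.** The contradiction is real and confined to one day per child. Followed as written, the post-treatment sentence puts an AE starting on stop + 1 into both the TEAE and the post-treatment category. The affected outputs are the overview by period and the post-treatment AE, severity and serious-AE summaries and listings.

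The effect on the primary endpoint is nil, provided the TEAE rule is applied as stated. The number of double-counted events in the other outputs cannot be derived from the documents, and it is zero if the inequality alone is programmed. This is a minor error in the wording of a stated rule, not a missing detail.

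**What to change.** In SAP 6.4, reword the post-treatment AE sentence so that it refers to a start date later than the stop date plus 1 day. Start the general post-treatment period at last dose + 2 days. Both then match the inequality already printed and the TEAE rule. Adding that each AE is assigned to exactly one period would remove remaining doubt.

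The cost is two edited lines, preferably before database lock. Programs written from the inequality need no change, TEAE counts do not move, and no clinical rule is touched. No protocol amendment is needed, because the protocol's TEAE window already agrees.

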#### Duration of adverse event:

(AE resolution date – AE onset or start date ) +1

#### Treatment Emergent Adverse Event (TEAE):

Document: \\ieedc-vnasc01\BIOSdata\GSK\BRL25000\PPD  
Author: PPD

\Biostatistics\Documentation\SAP

Version Number: V1.0

Version Date: 18JUL2022

Template No.: CS\_TP\_BS016 Revision 6

Reference: CS\_WI\_BS005

Effective Date: 02Dec2019

During treatment Period + lag time of 1day.

**Onset Time Since 1st Dose (Days):**

If Treatment Start Date > AE Start Date:

Onset Time = AE Onset Date - Treatment Start Date

If Treatment Start Date  $\leq$  AE Onset Date:

Onset Time = AE Onset Date - Treatment Start Date +1

**Study/Treatment Period for Concomitant medication**

**Pre-Treatment Period:**

If con-med start date < date of Visit 1 (or con-med date is missing)

**On-Treatment Period:**

If Con-med start date < study treatment start date (or Con-med start date is missing) and con-med stop date  $\geq$  study treatment start date (or Con-med start date is missing), or

If study treatment start date  $\leq$  Con-med start date  $\leq$  study treatment stop date+1.

If the study treatment stop date is missing and the con-med start date is on or after the study treatment start date, then the con-med will be on-treatment.

If the con-med start or stop date is missing or partial, then the con-med will be considered on-treatment unless there is evidence to the contrary (e.g. month/year of con-med stop date is present and is before the month/year of study treatment start date).

**Post -Treatment Period:**

If con-med stop date is after the treatment stop date+1

Con-med Stop Date > Study Treatment Stop Date+1

**Definition of on-set for an Event:**

Con-med duration (Days):

Con-med Stop Date – Con-med Start Date + 1

Time Since 1st Dose (Days):

If Treatment Start Date > Con-med Start Date:

Time = Con-med Start Date - Treatment Start Date

---

Document: \\ieedc-vnasc01\BIOSdata\GSK\BRL25000\PPD\Biostatistics\Documentation\SAP

Author: PPD

Version Number: V1.0

Version Date: 18JUL2022

Template No.: CS\_TP\_BS016 Revision 6

Reference: CS\_WI\_BS005

Effective Date: 02Dec2019

If Treatment Start Date  $\leq$  Con-med Start Date:

Time = Con-med Start Date - Treatment Start Date +1

If Treatment Start Date or start date of Con-med is missing

Time = missing.

## 6.5. RETESTS, UNSCHEDULED VISITS AND EARLY TERMINATION DATA

For by-visit summaries, refer Section 6.6 (visit windows).

Listings will include scheduled, unscheduled, retest and early discontinuation data.

## 6.6. WINDOWING CONVENTIONS

The following visit window will be used for efficacy as well as safety assessment.

Visit	Target Days	Visit Window
Baseline	0	Prior to first dose of study medication
Visit 1	1	#1
On-therapy visit or OT visit	3	2-5
End of therapy visit or EOT visit	12	6-14
Interim visit recurrence	18	15-21
Follow-up visit	25	$\geq 22$

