4. STUDY DESIGN

4.1. Overall Design

This study is an open label, multicentre, non-comparative study. Participants will be children aged between 6 months to 12 years, presenting with ARTIs including AOM, ABRS and CABP.

At Preliminary Visit (Day 0) after signing the informed consent form by the parent/guardian and assent form by children between 7 to 12 years of age, a series of screening evaluations will be performed (Section 5.4.2) including laboratory and radiographic evaluations, in order to determine whether prospective study participant meets the inclusion criteria. Enrolled participants will receive supervised first dose of study intervention from the participant pack. Dosing will be accompanied by demonstration/instruction on reconstitution procedure, product handling, storage, and

accountability (Section 6.2). Additional information on the same will be included in Study reference manual.

Visit 1 can be completed on the same day as the preliminary visit (Day 0) if the laboratory test results and radiological evaluation [Only if needed by investigator's discretion] are available on the same day. All participants will receive Augmentin (ES)-600 at 90/6.4 mg/kg/day administered in two divided doses, every 12 hours with food for 10 days.

The incidence of protocol-defined diarrhoea will be determined from information collected from the Patient Diary cards, which will be appropriately translated for all languages required based on sites participating in the trial. Protocol-defined diarrhoea is:

- 3 or more watery stools in one day OR
- 4 or more loose/watery stools in one day OR
- 2 watery stools per day for two consecutive days OR
- 3 loose/watery stools per day for two consecutive days.

After a minimum of two treatment days (four doses) of study intervention has been taken, an 'on-therapy' (OT) visit will be scheduled between Day 3 and 5.

During this visit, the investigator/study coordinator shall assess safety (primary endpoint) and 'early clinical response' (secondary endpoint). Safety parameter includes treatment-emergent adverse events (TEAEs) for primary study objective. Additionally, clinical status, study intervention compliance, completion of Patient Diary cards, and concomitant medications use will also be assessed. The Investigator will assess safety parameters and clinical status whereas study coordinator will check other parameters with coordinated effort.

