5.4.3.2. On-therapy Visit (Days 3 to 5)

After a minimum of two treatment days (four doses) of study intervention has been taken, an ‘on-therapy’ (OT) visit will be scheduled between Day 3 and 5.

During this visit, the investigator / study coordinator shall assess safety (primary endpoint) and ‘early clinical response’(secondary endpoint). Safety parameter includes treatment-emergent adverse events for primary study objective. Additionally, clinical status, study intervention compliance, completion of Patient Diary cards, and concomitant medications use will also be assessed. The Investigator will assess safety parameters and clinical status whereas study coordinator will check other parameters with coordinated effort.

Hence, the following will be evaluated at the OT Visit:

- TEAE (primary endpoint)
- Early Clinical Response (secondary endpoint)

- Incidence of Protocol-defined diarrhea (secondary endpoint)
- Vital signs
- Local examination
- Concomitant medication
- Bowel movements
- Physical examination (assessments of the skin, cardiovascular, respiratory, gastrointestinal, and neurological systems, height and weight)
- Clinical assessment

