# Visit 1 will be considered as baseline for patient diary card assessments if subject does not have patient diary data prior to Visit 1.

\* Interim visit (< 24 hrs of notification) is required only if subject having clinical failure or PDD or server AE of SAE after OT visit prior to EOT visit. In this case all assessment of interim visit will be mapped to EOT visit as scheduled.

If there is more than one record for a given parameter within a specific visit window, then the non-missing record closest to the target day will be summarized. If there are multiple records on the same day for a parameter, then the average value will be considered for continuous parameters, and the worst value will be considered for the categorical parameters.

Study treatment discontinuation and unscheduled visit will also be considered for deriving the visit window for parameters.

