#### Definition of clinical responses

Early or Primary Clinical Response will be defined using following criteria:

Table 3:

Success	Clinical cure	Sufficient resolution or improvement of the signs and symptoms such that no additional antibiotic therapy is indicated.
	Improvement	Improvement in at least 1 presenting sign/symptoms. No additional antibiotic indicated.
Failure	Clinical failure	Non-improvement or deterioration in any sign/symptoms after 2 or more days of therapy. Additional antibiotic therapy is indicated.
	Unable to determine	A valid assessment of clinical outcome could not be made (eg, participant did not attend or consent to clinical examination or lost to follow-up).

The proportion of early and primary response will be calculated as follows-

- Proportion of early response = The number of subject who is categorized as success (clinical cure or improvement) at on therapy (OT) visit / the number of subjects in ITT population
- Proportion of primary response = The number of subject who is categorized as success (clinical cure or improvement) at end of therapy (EOT) visit/ the number of subjects in ITT population

Secondary Clinical response will be described using following criteria:

Table 4:

Document:	\\ieedc-vnasc01\BIOSdata\GSK\BRL25000\PPD	Biostatistics\Documentation\SAP
Author:	PPD	Version Number: V1.0 Version Date: 18JUL2022

Template No.: CS\_TP\_BS016 Revision 6

Reference: CS\_WI\_BS005

Effective Date: 02Dec2019

Success	Persistent clinical cure*	Sufficient resolution of signs/symptoms for those Subjects who were clinically cured or improved at the end of therapy. No additional antibiotic indicated.
Failure	Clinical recurrence	Reappearance of signs/symptoms for those Subjects who were clinically cured or improved at the end of therapy. Additional antibiotic therapy is indicated.
	Unable to determine	A valid assessment of clinical outcome could not be made (eg, participant did not attend end of therapy visit, or extenuating circumstances or lost to follow-up).

\* Subjects who showed 'improvement' at EOT (i.e., clinical 'success') and remained same at FU without requiring additional intervention, will be categorized as 'persistent clinical cure'.

The proportion of secondary response will be calculated as follows-

- Proportion of secondary response = The number of subject who is categorized as success (persistent clinical cure) at follow-up (FU) visit / the number of subjects in ITT population

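### The closest-to-target rule in SAP 6.6 gives the scheduled visit no priority, so a second response rating can replace or tie with a late but compliant EOT or OT rating

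*SAP*

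**What the plan says.** **Protocol.** In section 4.1 the on-therapy (OT) "visit will be scheduled between Day 3 and 5", and section 5.4.3.2 places it "After a minimum of two treatment days (four doses) of study intervention has been taken". EOT is at Day 12-14 (sections 4.1 and 5.4.4). The Schedule of Activities (section 1.3) collects early clinical response at OT only, and primary clinical response at both the pre-EOT interim visit and EOT.

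**SAP endpoints.** Sections 2.1 and 15.1 repeat Day 3-5 and Day 12-14. Section 3.3 declares no change in analysis from the protocol.

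**SAP 6.6.** "The following visit window will be used for efficacy as well as safety assessment". The row "On-therapy visit or OT visit" has target Day 3 and window Day 2-5. The row "End of therapy visit or EOT visit" has target Day 12 and window Day 6-14. If a window holds more than one record for a parameter, "then the non-missing record closest to the target day will be summarized". Several records on the same day are resolved by taking the worst category. The section also states: "Study treatment discontinuation and unscheduled visit will also be considered for deriving the visit window for parameters". A note maps interim-visit assessments to EOT and does not limit this to children withdrawn at that visit.

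**The concern.** The SAP windows open earlier than the protocol's: one day earlier for OT and six days earlier for EOT. The selection rule then treats every eligible record alike. Because each target is the first permitted day, a scheduled visit held later in its allowed range is further from target than some records that precede the range altogether.

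Two things are missing: a statement that the scheduled rating comes first, and a tie rule for records on different days. Without them, the value analysed as the EOT response need not be the endpoint defined in SAP 15.1, and ties would be settled by a programming choice.

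The replacement would not be random with respect to outcome. Children are called to the pre-EOT interim visit for worsening, diarrhoea meeting the protocol definition, or a severe or serious adverse event (Protocol 5.4.3.3).

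**Working it through.** The plan states no figure on this point to reproduce. The check applies the SAP 6.6 rule directly.

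**Inputs.** Targets (3 and 12) and windows (2-5 and 6-14) come from SAP 6.6. Permitted scheduled days (3-5 and 12-14) come from Protocol 4.1. The denominator is the ITT population (SAP 15.1), with 310 children planned: 136 AOM, 106 ABRS and 68 CABP (SAP 6.8).

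**Step 1: distances.** Distance = |day − target|, and the smallest is selected.

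- OT, target 3: Day 2 = 1, Day 3 = 0, Day 4 = 1, Day 5 = 2.
- EOT, target 12: Day 9 = 3, Day 10 = 2, Day 11 = 1, Day 12 = 0, Day 13 = 1, Day 14 = 2. Days 6-8 are further away (6, 5 and 4).

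**Step 2: an extra rating from before the protocol range against the scheduled rating.**

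| Extra rating | Scheduled on first day (3 or 12) | Scheduled on middle day (4 or 13) | Scheduled on last day (5 or 14) |
|---|---|---|---|
| OT Day 2 | kept (0 vs 1) | tie (1 vs 1) | replaced (2 vs 1) |
| EOT Day 11 | kept (0 vs 1) | tie (1 vs 1) | replaced (2 vs 1) |
| EOT Day 10 | kept (0 vs 2) | kept (1 vs 2) | tie (2 vs 2) |
| EOT Days 6-9 | kept | kept | kept (2 vs 3 or more) |

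The worst-category rule settles same-day records only, so none of these ties is resolved.

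**Step 3: would narrowing the windows cure it?** With windows 3-5 and 12-14, the Day 2, 10 and 11 records drop out. An unscheduled Day 12 rating (distance 0) still beats a scheduled Day 13 or 14 rating (1 or 2), and Day 13 beats Day 14. At OT, Day 3 beats Days 4 and 5, and Day 4 beats Day 5. Narrowing is therefore not sufficient.

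**Step 4: effect of one reversed rating.**

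- Overall: 1/310 = 0.32 percentage points
- AOM: 1/136 = 0.74
- ABRS: 1/106 = 0.94
- CABP: 1/68 = 1.47

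The documents give no count of children with two ratings in a window. As an assumed range only, 1 to 10 reversals, all in the same direction, would move the overall proportion by 1/310 = 0.3 to 10/310 = 3.2 points.

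**The case against.** The strongest reply is that duplicates are hardly planned for.

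- **OT.** Early response is collected only at OT, and selection works on non-missing records for the same parameter, so a Day 2 vital sign cannot displace a Day 5 response rating. This stands: a Day 2 duplicate is unlikely.
- **EOT.** When a child is withdrawn at the interim visit, that visit is the EOT visit under the protocol, and the SAP maps it so. This also stands. It leaves the child who is rated at an interim visit and not withdrawn. Protocol 5.4.3.3 makes withdrawal follow confirmation of the event and leaves it to the investigator, so that child can have two ratings.
- **Window width.** Analysis windows wider than scheduling windows are an ordinary choice, because they keep off-schedule visits analysable. This stands too. Under Day 12-14, a scheduled EOT visit attended on Day 11 would be lost. With an ITT denominator (SAP 15.1) and no imputation (SAP 7.3), that child could not count as a success.

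A reader might also infer that a Day 2 rating can never be a clinical failure, because the definition reads "Non-improvement or deterioration in any sign/symptoms after 2 or more days of therapy". That goes too far. With 12-hourly dosing from Day 1, four doses over two treatment days can be complete late on Day 2.

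**Conclusion.** The point holds as a gap in the selection rule. SAP 6.6 allows a protocol-compliant scheduled rating to be replaced when it falls on the last permitted day, and leaves some pairs unresolved (Day 2 with 4, Day 11 with 13, Day 10 with 14). EOT is where this could realistically happen.

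Three stronger readings are not supported:

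- **Any Day 2 or Day 11 record displaces the scheduled rating.** It does so only against Day 5 or Day 14, and only if it carries a rating of the same endpoint.
- **The whole early part of the EOT window is at fault.** Day 6-9 ratings never displace a scheduled Day 12-14 rating, and early ratings from withdrawn children are intended as EOT.
- **A shift of a particular size should be expected.** The documents give neither how often two ratings occur nor how often they disagree.

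The firm size is per child: 0.32 points overall and up to 1.47 points in CABP, assuming planned enrolment and the full ITT denominator. These endpoints are secondary and no formal hypothesis is tested (Protocol 9.1), so this is a minor correction.

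**What to change.** In SAP 6.6, for the clinical response endpoints:

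1. Use the rating from the scheduled OT or EOT visit whenever one exists.
2. Use a pre-EOT interim or discontinuation rating as EOT only when the child was withdrawn from study intervention at that visit, and align the interim-visit mapping note with this.
3. Keep the wider windows only so that a scheduled visit attended off-schedule remains analysable.
4. State a tie-break for records on different days, for example the later rating, or the worse one in line with the same-day rule.

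In SAP 3.3, declare that the analysis windows are wider than the protocol's visit days.

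The rule should say that it selects a rating only. Failure imputed under the composite strategy in SAP 2.2, and failure by definition after alternate antibiotics (Protocol 6.5), remain as they are.

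The cost is a few sentences and a small programming change before database lock. Visits, data collection and sample size are unaffected.

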7.3. Lost to Follow Up

A participant will be considered lost to follow-up if he or she repeatedly fails to return for scheduled visits and is unable to be contacted by the study site.

The following actions must be taken if a participant fails to return to the clinic for a required study visit:

- The site must attempt to contact the participant and reschedule the missed visit as soon as possible and counsel the participant on the importance of maintaining the assigned visit schedule and ascertain whether the participant wishes to and/or should continue in the study.
- Before a participant is deemed lost to follow up, the Investigator or designee must make every effort to regain contact with the participant (where possible, 3 telephone calls on 3 consecutive days and, if necessary, a certified letter to the

participant's last known mailing address or local equivalent methods). These contact attempts should be documented in the participant's medical record.

- Should the participant continue to be unreachable, he/she will be considered to have withdrawn from the study.

Discontinuation of specific sites or of the study are handled as part of [Appendix 1](#).

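### Day-only windows in SAP 6.6 remove a scheduled EOT visit held after Day 14 from the EOT analysis, so an observed primary response is discarded

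*SAP*

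**What the plan says.** SAP 6.6 introduces its window table with the rule "The following visit window will be used for efficacy as well as safety assessment". Each post-baseline row after Visit 1 is defined by study day only:

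- On-therapy: Days 2–5, target Day 3.
- "End of therapy visit or EOT visit": Days 6–14, target Day 12.
- "Interim visit recurrence": Days 15–21, target Day 18.
- Follow-up: Day 22 or later, target Day 25.

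SAP 6.5 sends by-visit summaries to this table. The notes under the table add: "Study treatment discontinuation and unscheduled visit will also be considered for deriving the visit window for parameters". They contain one exception, for the interim visit held between OT and EOT because of failure, PDD or a severe or serious AE: "In this case all assessment of interim visit will be mapped to EOT visit as scheduled".

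SAP 15.1 defines the primary response proportion as the number of children "categorized as success (clinical cure or improvement) at end of therapy (EOT) visit/ the number of subjects in ITT population". SAP 7.3 imputes no missing data. SAP Appendix 3 prints a PROC FREQ call with an exact binomial interval and no MISSING option.

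Protocol 1.3 schedules EOT on Day 12 to 14 and keeps Day 15 to 21 for an extra visit that is needed only if disease recurs. When a child misses a visit, Protocol 7.3 asks the site to "reschedule the missed visit as soon as possible".

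**The concern.** The recurrence visit is triggered by an event, but its analysis window is a plain range of days that takes in any visit held then. An EOT visit that slips by a day or two is foreseeable: the scheduled range is three days wide, sites are told to rebook missed visits, and both documents expect COVID-related disruption (Protocol 10.6.2, SAP 9.1 and 16.6). The only interval extension in Protocol 10.6.2 concerns sample collection at follow-up.

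A child examined on Day 15 and rated cured would then have a valid rating in the database and nothing in the EOT analysis. The window is also lopsided. It accepts visits up to six days before the Day 12 target but none after Day 14, and early failures are expressly mapped into EOT. At stake is the reported EOT success proportion, overall and by indication. A follow-up visit held on Day 21 meets the same problem for the secondary response.

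**Working it through.** **Denominators.** The plan states no figure for this issue, so the first check is on the sample sizes. With 310 children in the ratio 18:9:14 (sum 41), 310 × 18/41 = 136.1, 310 × 9/41 = 68.0 and 310 × 14/41 = 105.9. These reproduce the plan's 136 AOM, 68 CABP and 106 ABRS.

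**Window by day.** Applying the SAP 6.6 table literally:

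| Day of visit | Assigned to |
|---|---|
| 6–14 | EOT |
| 15–21 | Interim visit recurrence |
| 22 or later | Follow-up |

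The SAP 6.6 exception covers only the interim visit before EOT. No rule returns a late scheduled EOT visit to EOT. If that visit holds the child's only primary-response rating, the EOT window is empty.

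**Cost of one lost success.** Under the SAP 15.1 formula it is 100/N points: 100/310 = 0.32 overall, 100/136 = 0.74 in AOM, 100/106 = 0.94 in ABRS and 100/68 = 1.47 in CABP.

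**Size under assumptions.** The documents give neither the EOT success rate nor the share of late visits. Let *s* be the true success rate and *f* the late share, with lateness unrelated to outcome. Late children L = 310*f* (rounded), lost successes = L × *s* (rounded), and loss in points = 100 × lost/310.

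| *s* | *f* = 1% (L = 3) | 2% (L = 6) | 5% (L = 16) | 10% (L = 31) |
|---|---|---|---|---|
| 80% | 2 lost, 0.6 | 5 lost, 1.6 | 13 lost, 4.2 | 25 lost, 8.1 |
| 85% | 3 lost, 1.0 | 5 lost, 1.6 | 14 lost, 4.5 | 26 lost, 8.4 |
| 90% | 3 lost, 1.0 | 5 lost, 1.6 | 14 lost, 4.5 | 28 lost, 9.0 |
| 95% | 3 lost, 1.0 | 6 lost, 1.9 | 15 lost, 4.8 | 29 lost, 9.4 |

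**One case with exact (Clopper–Pearson) intervals**, *s* = 90% and *f* = 5%:

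- Late EOT visits keep their label: 279/310 = 90.0% (86.1–93.1).
- Literal windows with the SAP 15.1 denominator: (279 − 14)/310 = 265/310 = 85.5% (81.1–89.2).
- Literal windows with missing responses dropped, as the Appendix 3 code does by default: 265/(310 − 16) = 265/294 = 90.1%.

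The last two lines differ only in the denominator. Both discard 16 observed ratings.

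**Secondary response.** SAP 15.1 counts successes at the follow-up visit over the ITT population, and the follow-up window opens on Day 22. A follow-up visit on Day 21 is filed in the recurrence row. SAP 15.1.1.1 plans response summaries at OT, EOT and follow-up only, so that rating reaches no response table.

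**The case against.** The strongest defence is that the cut-off is the protocol's own. Protocol 8.1 ties EOT success to the scheduled visit on Day 12–14, and non-attendance is classed as unable to determine, which is a failure. On that view a Day 15 rating lies outside the endpoint and counting it as a non-success is the planned conservative rule. Part of this stands: Day 14 is the protocol's limit, which justifies flagging late ratings and argues against simply stretching the window. It does not dispose of the point. The SAP already takes ratings from Days 6 to 11 as EOT, so it is not enforcing Day 12–14. Unable to determine means that no valid assessment could be made, which does not describe a child who was examined on Day 15.

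Second, the downward direction is not certain. It follows from the SAP 15.1 formula, whereas the Appendix 3 code would drop the child and leave the proportion almost unchanged in the example. SAP 2.2 further limits the calculation to children with at least 80% compliance, although a compliant cured child remains in that set. This objection stands: the size of any bias depends on a denominator that the SAP does not settle.

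Third, a reader might infer that the recurrence count is inflated by children who never relapsed. The documents do not support that. The schedule of activities records primary and secondary response as separate items, SAP 6.6 selects records parameter by parameter, and no response table is planned for the Day 15–21 row. What could be affected there is mainly by-visit data such as vital signs (SAP 16.5).

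Finally, Protocol 7.3 is a lost-to-follow-up procedure and gives no late-visit rate, and Protocol 8 calls adherence to the schedule essential. Late visits may be few.

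**Conclusion.** The gap in the rule is real. On the literal text, a scheduled EOT visit held on Day 15–21 is filed as a recurrence visit and one held on Day 22 or later as Follow-up. If no other primary-response record falls in Days 6–14, an observed outcome is discarded.

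Under the ITT formula the proportion can only fall. Over assumed success rates of 80–95%, the loss is about 0.6–1.0 points if 1% of visits are late and 4.2–4.8 points if 5% are. It would be tempting to conclude that the EOT response will be materially biased downward. The documents do not support that as a forecast, because both rates are assumptions and the printed code implies a different denominator.

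The endpoint is secondary and descriptive, with no formal hypothesis, so the sample size, error rates and primary safety endpoint are untouched. The change is worth making before database lock because it is cheap and needs no new data.

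**What to change.** In SAP 6.6:

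1. Assign early, primary and secondary clinical response by nominal eCRF visit, keeping the existing mapping of the pre-EOT interim visit to EOT.
2. Use day windows only for unscheduled records.
3. Reserve the recurrence row for visits flagged as recurrence.
4. State that a child with no EOT rating stays in the denominator as unable to determine, and make the Appendix 3 code agree.
5. Flag EOT ratings taken after Day 14 and add a sensitivity summary restricted to ratings up to Day 14.

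Do not extend the EOT window to Day 21. That would admit ratings up to a week past the protocol's limit and overlap the interval kept for recurrence.

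The cost is a few lines of SAP text, a programming rule and one extra summary. The downside is that a few ratings in the main summary will fall outside the protocol's Day 12–14 range; the flag and the sensitivity summary make them visible.
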